5.1 Imputation rules

5.1.1 Study drug

The study drug administration date should be complete since it's taken in the hospital. In case missing or partial, the visit date will be used as the study drug administration date.

5.1.2 AE date imputation

The following missing dates will not be imputed

- Missing AE start dates
- AE start dates missing the year
- Partial/missing AE end dates

For other type of partial missing start dates, rules specified in [Tables 5-1 to 5-3](#) will be used

Table 5-1 AE/Treatment Date Abbreviations

	Day	Month	Year
Partial Adverse Event Start Date	<not used>	AEM	AEY
Treatment Start Date (TRTSTD)	<not used>	TRTM	TRTY

[Table 5-2](#) describes the possible combinations and their associated imputations. The upper text indicates the imputation (NC, A, B, C etc.) and the lower text the relationship of the AE start date to the treatment start date (TRTSTD).

Table 5-2 Imputation algorithm

	AEM MISSING	AEM < TRTM	AEM = TRTM	AEM > TRTM
AEY MISSING	NC Uncertain	NC Uncertain	NC Uncertain	NC Uncertain
AEY < TRTY	(D) Before TRTSTD	(C) Before TRTSTD	(C) Before TRTSTD	(C) Before TRTSTD
AEY = TRTY	(B) Uncertain	(C) Before TRTSTD	(B) Uncertain	(A) After TRTSTD
AEY > TRTY	(E) After TRTSTD	(A) After TRTSTD	(A) After TRTSTD	(A) After TRTSTD

The legend to the above table is shown in [Table 5-3](#).

Table 5-3 Imputation algorithm legends

Relationship	
Before TRTSTD	Indicates AE start date prior to Treatment Start Date
After TRTSTD	Indicates AE start date after Treatment Start Date
Uncertain	Insufficient to determine the relationship of AE start date to Treatment Start Date
Imputation calculation	
NC / Blank	No convention/imputation
(A)	01MONYYYY
(B)	TRTSTD+1
(C)	15MONYYYY
(D)	01JULYYYY
(E)	01JANYYYY

Few examples are shown in [Table 5-4](#).

Table 5-4 Example scenarios

Partial AE start date	Treatment start date	Relationship with TRTSTD	Imputation Calculation	Imputed Date
12mmyyyy	20OCT2001	Uncertain	NC	<blank>
ddmmm2000	20OCT2001	Before	(D)	01JUL2000
ddmmm2002	20OCT2001	After	(E)	01JAN2002
ddmmm2001	20OCT2001	Uncertain	(B)	21OCT2001
ddSEP2001	20OCT2001	Before	(C)	15SEP2001
ddOCT2001	20OCT2001	Uncertain	(B)	21OCT2001
ddNOV2001	20OCT2001	After	(A)	01NOV2001

5.1.3 Concomitant medication/non-drug therapy date imputation

Missing concomitant dates will be imputed similar as to AE dates.

5.1.3.1**5.1.3.2 Other imputations**

NA

5.1.4 Visit windows

When visit windows are used, all visits will be re-aligned, i.e., they will be mapped into one of the visit windows. E.g., if the Day 4 visit of a patient is delayed and occurs on Day 7, say, it will be re-aligned to visit window Day 8. In the case of major deviations from the visit schedule, or due to unscheduled visits, several assessments of a patient may fall in a particular visit window (either scheduled or unscheduled). Statistical approaches to handle multiple assessments in a given visit window are specified below.

- Of note, patients are allowed to have gaps in visits. All data collected will be displayed in listings.
- Lower limit and upper limit of the Day 29 visit is set to be Day 25 and Day 33 respectively, according to the protocol visit schedule since this is the primary analysis timepoint.
- The following rules are used to determine the window for other visits post baseline:
 - “Lower limit” = “upper limit of prior applicable visit” + 1.
 - “Upper limit” = “target day of current visit” + integer part of (“target day of next applicable visit” – “target day of current visit”)/2 with the exception of Day 29
 - No upper limit for Day 43 visit
 - Upper limit of Day 15 is one day before the lower limit of Day 29

For assessments that are scheduled to be performed only once on a day, [Table 5-5](#) describes the analysis windows mapping to visits (not just scheduled visits) based on study days alone. For the assessments that may be performed on multiple timepoints on a day, [Table 5-6](#) describes the analysis windows mapping to visits based on study day and time. Repeat and/or unscheduled visits (which will be numbered in the database according to new NCDS standards) will be mapped for analysis purposes in the same way. If there are multiple measurements within an analysis window, the conventions defined in [Table 5-7](#) will be used to determine the appropriate measurement to be selected for analysis.

The mapped visits will be used in the by visit analyses. However, the listings will show the collected data regardless of used in the by visit analyses.

Table 5-5 Analysis visit windows based on study days alone

Analysis Visit	Target Day	Analysis window for assessment group		
		Vital signs/ Hematology/	Chemistry/ Urinalysis	Thyroid function
Baseline	1	Up to Day 1	Up to Day 1	up to day 1
Day 2	2	Day 2	NA	NA
Day 3	3	Day 3	NA	NA
Day 4	4	Day 4	NA	NA
Day 5	5	Days 5 - 6	NA	NA
Day 8	8	Day 7 - 11	NA	NA
Day 15	15	Day 12 - 24	Day 2 - 29	NA
Day 29	29	Day 25 - 33	NA	NA
Day 43/End of study	43	Day 34 and above	Day 30 and above	Day 2 and above

Table 5-6 Analysis visit windows based on study day and time

Analysis Visit	Analysis timepoint	Analysis window for assessment group			
		Temperature	Parasite count	ECG	Rich and Sparse PK
Baseline	0 hrs	up to 0 hrs	up to 0 hrs	up to 0 hrs	up to 0 hrs
Day 1	1 hrs	NA	NA	NA	> 0 - 2 hrs
	3 hrs	NA	NA	>0 - 4 hrs	> 2 - 4 hrs
	6 hrs	>0 - 9 hrs	>0 - 9 hrs	>4 - 12 hrs	>4 - 9 hrs
	8 hrs	NA	NA	NA	NA
	12 hrs	>9 - 15 hrs	>9 - 18 hrs	NA	>9 - 15 hrs
	18 hrs	>15 - 21 hrs	NA	>12 - 21 hrs	>15 - 21 hrs
Day 2	24 hrs	>21 - 27 hrs	>18 hrs to 30 hrs	>21 - 25 hrs	>21 - 25 hrs
	27 hrs	NA	NA	>25 – 28 hrs	>25 - 28 hrs
	30 hrs	>27 - 33 hrs	NA	>28 - 39 hrs	>28 - 33 hrs
	36 hrs	>33 - 42 hrs	>30 - 42 hrs	NA	>33 - 42 hrs
Day 3	48 hrs	>42 - 60 hrs	>42 - 60 hrs	>39 – 49 hrs	>42 - 49 hrs
	51 hrs	NA	NA	>49 – 52 hrs	>49 - 52 hrs
	54 hrs	NA	NA	>52 – 61 hrs	>52 - 63 hrs
	60 hrs	NA	NA	NA	NA
	68 hrs	NA	NA	>61 – 70 hrs	NA
Day 4	72 hrs	>60 hrs to Day 4	>60 hrs to Day 4	>70 hrs to Day 5	>63hrs to Day 4
Day 5	NA	Day 5 - 6	Day 5 - 6	NA	Day 5 - 6
Day 8	NA	Day 7 – 11	Day 7 – 11	Day 6 -25	Day 7 – 11
Day 15	NA	Day 12 - 24	Day 12 - 24	NA	Day 12 and above
Day 29	NA	Day 25 - 33	Day 25 - 33	NA	NA
Day 43/End of study	NA	Day 34 and above	Day 34 and above	Day 26 and above	NA

Table 5-7 Rules for flagging variables

Timing of measurement	Type of data	Rule
Baseline	All data	The last measurement made prior to administration of the first dose of study treatment – note this may include measurements taken on the day of randomization. If a patient did not receive any dose of study treatment then the randomization date will be used.
Post-baseline efficacy	parasite count and temperature	The measurement closest to the target day/time will be used. In the event two measurements are taken equally apart, the first one will be used.(.)
Post-baseline safety	Summary visit information (e.g. lab, ECG, etc.)	The measurement closest to the target day/time will be used. In the event two measurements are taken equally apart, the first one will be used.
Post-baseline safety	Notable abnormalities (e.g. lab, ECG, VS)	The most extreme measurement in the window will be used. Note this means a patient can have a notably high and notably low measurement within a window

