#### 9.5.1.1 PCR-corrected ACPR and uncorrected ACPR

At each visit, the mean ACPR rate with 95% confidence intervals will be provided using Pearson-Clopper method for each treatment group.

Data will be handled as follows:

- Treatment failures after 7 days (i.e., Day 8) due to reinfection based on PCR genotyping are not considered as failure for PCR-corrected analyses.
- For parasitological uncorrected ACPR, patients will be treated as failure on and after the visit when a new infection (i.e., reinfection) with *P. falciparum* or other species is detected.
- Patients who received rescue medication for the treatment of *P. falciparum* malaria (except for the treatment of a new infection) will be considered treatment failures (from the day of rescue use onwards). Patients who received other concomitant medication having an effect on malaria for reasons other than rescue therapy e.g. for the treatment of *P. vivax* or for the treatment of *P. falciparum* gametocytes (e.g. primaquine, certain

antibiotics (sulfonamides, tetracycline, etc.) will be considered in the analysis as if they had not taken the drug.

- Patients will be counted as failure at a visit (e.g., Day 15, etc.) if (a) they did not have a parasite count at that visit unless these patients could be classified as cured based on absence of parasitaemia at a later time (e.g., Day 29), or (b) they did not have valid PCR evaluations at baseline and the visit if parasitaemia was present at that time (e.g., Visit Day 15).

In addition, PCR-corrected ACPR rate will be calculated and plotted using the Kaplan-Meier method for each treatment group in the FAS (see [Section 9.4.4](#)).

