2.1.1.2 Definition of ACPRs

Uncorrected ACPR at Day X where X=15, 29, or 43

- A patient is considered as non-responder at Day X if the patient experiences an ETF, LCF from Day 5 to Day X, or LPF from Day 8 to Day X.
- A patient is also considered as non-responder if the parasite is not cleared by Day X unless the patient discontinues the study prior to Day X without ETF or LCF or LPF, in which case the response is considered as missing.
- A patient is considered as responder (Uncorrected ACPR) at Day X if the patient is not classified as a non-responder at Day X and the patient has a malaria blood film showing absence of parasite at Day X or later if Day X is missing.
- The response for a patient is considered as missing/underdetermined if the patient is not classified as a non-responder and the malaria blood film result at Day X is missing and not followed by a subsequent negative result.

PCR-corrected ACPR at Day X where X=15, 29, or 43

- A patient is considered as non-responder at Day X if the patient experiences an ETF or LCF from Day 5 to Day 7.
- A patient is also considered as non-responder if the parasite is not cleared by Day X unless the patient discontinues the study prior to Day X without ETF or LCF or LPF, in which case the response is considered as missing,
- A patient is considered as non-responder at Day X if the patient has a parasite recrudescence from Day 8 to Day X
- A patient is considered as responder (corrected ACPR) at Day X if the patient is not classified as a non-responder by Day 7 and has a new infection or negative results from Day 8 to Day X based on PCR genotyping unless that the patient did not have parasites cleared prior to the new infection, in which case the patient is considered as non-responder.
- A patient is considered as responder at Day X if the patient is not classified as a non-responder at Day X and the patient has a malaria blood film showing absence of parasite at Day X or later if Day X is missing.
- The response for a patient is considered as missing/underdetermined if
 - The patient, not classified as non-responder at Day X, has parasite present from Day 8 to Day X for which the PCR genotyping of recrudescence or new infection is not determined.
 - The patient is not classified as a non-responder at Day X and the malaria blood film result at Day X is missing and not followed by a subsequent negative result.

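### The SAP's Day 43 parasite-count window opens at Day 34, five days before the protocol's visit window, so a negative last film on Days 34–38 is scored as a Day 43 response and the missing-film rule is not triggered

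*SAP*

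**What the plan says.** **Windows.** SAP 5.1.4 starts each post-baseline window on the day after the previous window closes. Day 29 is the exception: its window "is set to be Day 25 and Day 33 respectively, according to the protocol visit schedule since this is the primary analysis timepoint". For Day 43 the SAP adds "No upper limit for Day 43 visit", and the parasite-count column of Table 5-6 gives "Day 34 and above". Unscheduled and delayed visits are mapped in the same way, and "The mapped visits will be used in the by visit analyses". Where several counts fall in one window, Table 5-7 takes the one closest to the target day.

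**Protocol schedule.** The visit tables (for example Table 6-2) give Day 43 a window of ±4 days. That visit is labelled as both the end of follow-up and the premature-withdrawal visit.

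**Response.** Under SAP 2.1.1.2 a patient who is not already a non-responder is a responder if "the patient has a malaria blood film showing absence of parasite at Day X or later if Day X is missing".

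**Missing films.** Protocol 9.5.1.1: "Patients will be counted as failure at a visit (e.g., Day 15, etc.) if (a) they did not have a parasite count at that visit", with an exception for a later negative film. SAP 2.7.2.1 has the same rule and the same exception. SAP 2.7.2.2 also uses the presence of a Day 43 film to define who enters the LCF and LPF denominators.

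**Declared changes.** SAP Section 4 lists none.

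**The concern.** ACPR at Day 43, corrected and uncorrected, is the last efficacy time point. It is a named secondary endpoint and goes to the DMC at the end of Part A (SAP Table 2-8). Its purpose is to pick up late recurrence. If a film taken on Day 34 can stand as the Day 43 film, the patient is credited with staying free of parasites through a period in which nobody looked. The plan has a rule for a patient with no film at a visit and no later negative film, but the early opening of the window means that rule is never reached for these patients. The LCF and LPF denominators gain the same patients as non-failures, which slightly lowers those proportions.

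**Working it through.** **Inputs.** Visit targets Days 5, 8, 15, 29 and 43 and the window rule (SAP 5.1.4); Day 43 ±4 days (protocol Table 6-2); about 50 randomised and 42 per-protocol patients per KAF156/LUM-SDF arm, 25 and 21 for control (protocol 9.8); expected drop-out 16% (protocol Section 4).

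**1. Reproduce the SAP's window.** The rule is: lower limit = previous upper limit + 1; upper limit = target + integer part of half the gap to the next target. Day 15 is cut at Day 24, Day 29 is fixed at Days 25–33, and Day 43 is left open.
- Day 5: 5 to 5 + int(3/2) = 6
- Day 8: 7 to 8 + int(7/2) = 11
- Day 15: 12 to 24
- Day 29: 25 to 33
- Day 43: 33 + 1 = 34 onwards

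This matches Table 5-6, so Day 34 follows from the rule and is not a typing error. Without the Day 29 exception, Day 43 would open at 29 + int(14/2) + 1 = 37.

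**2. Compare with the protocol visit window.** 43 − 4 = 39 and 43 + 4 = 47. The SAP opens 39 − 34 = 5 days earlier, on Days 34–38.

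**3. Who is affected.** A film on Days 39–47 is at most 4 days from target and a film on Days 34–38 is 5 to 9 days away, so Table 5-7 always prefers the former. The early opening matters only for a patient whose last film falls on Days 34–38, is negative, and follows no earlier failure. This could be a withdrawal, an unscheduled visit, or a Day 29 visit attended late.

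**4. Time not observed.** Last film on Day 34: (43 − 34)/(43 − 29) = 9/14 = 64%. Last film on Day 38: 5/14 = 36%. For comparison, Day 39, which the protocol window accepts, leaves 4/14 = 29%.

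**5. Effect per patient.** Moving one patient from responder to non-responder changes the rate by 1/n: 1/50 = 2.0 points, 1/42 = 2.4; for control 1/25 = 4.0 and 1/21 = 4.8. As an illustration with assumed counts, 40/42 is 95.2% (exact 95% CI 83.8–99.4); with one patient reclassified, 39/42 is 92.9% (80.5–98.5); with two, 38/42 is 90.5% (77.4–97.3).

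**6. How many patients.** The documents do not say. If the 16% drop-out is spread evenly over 42 days (assumption), the five-day band holds 16% × 5/42 = 1.9%, and 0.019 × 50 ≈ 1 patient. This supposes that every leaver in the band has an exit film and that every such film is negative, so under even drop-out it is a ceiling.

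**7. Direction.** A positive *P. falciparum* film on Days 34–38 is an uncorrected failure under either window. Relative to the missing-film rule, the early opening can therefore only raise the Day 43 rate.

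**The case against.** Several points on the other side are sound.

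- **The ±4 days is a scheduling window.** The protocol sets no analysis window, and the Day 43 visit doubles as the withdrawal visit, so a withdrawal film could be read as a count at that visit. A reader might infer that the protocol expressly scores a Day 34–38 leaver as failure; that is too strong. But the SAP itself turned the scheduling window into the analysis window for Day 29. The withdrawal label would equally admit a film from Day 20, which the SAP does not map to Day 43.
- **The missing-film rules do not differ.** A reader might infer that the SAP relaxed the protocol's rule. Both documents have the same one; what differs is the mapping that decides when a film is missing.
- **Scoring leavers as failures is itself biased, downwards.** The gap from the missing-film rule is not the gap from the true rate. This stands.
- **An unaffected analysis is already planned.** SAP 2.5.4.1, 2.5.4.2 and 2.7.2.1 provide Kaplan-Meier estimates in the FAS, which censor patients without failure or another censoring event at the last parasite assessment. This stands, but the exact binomial proportions are still reported.
- **Day 15 also has a wide window.** Its lower limit is one day early (Day 12 against 15 − 2 = 13), and films after Day 17 would count anyway as later negative films. At Day 43 there is usually no later film to fall back on, so the window matters more there.

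**Conclusion.** The point holds as a minor, undeclared windowing choice that favours response at Day 43. It touches the corrected and uncorrected Day 43 ACPR proportions and the LCF/LPF denominators. A reader might infer that it reaches the cohort success criterion. It does not: that criterion uses corrected ACPR at Day 29, whose window agrees with the protocol, and the secondary endpoints carry no pre-specified hypotheses.

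The firm size is 2.0 to 2.4 points per affected patient in a KAF156/LUM-SDF arm. A reader might also infer a routine shift of several points. The documents do not support that: under even drop-out the expectation is about one patient in 50 at most, and 5% of an arm would need 5/16 = 31% of all drop-outs to fall within five days. Clustered drop-out could exceed the even-spread figure, but nothing in the documents points to it. That patients in the band have a film at all is inferred from the protocol's instructions for premature withdrawal (5.7.3 and Section 6), because Table 6-1 is not shown in the text available.

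**What to change.** Add a sentence to SAP 5.1.4, with cross-references in 2.1.1.2 and 2.7.2.2:

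- For corrected and uncorrected ACPR at Day 43, and for the Day 43 film in the LCF/LPF denominators, count only films from Day 39 onwards; a negative film there is needed to establish response.
- Use films on Days 34–38 to detect failure and, as now, as a later film when Day 29 is missing.
- Keep the existing mapping for all other by-visit summaries.

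If the wider window is kept instead, declare it in SAP Section 4 and report the Day 39 rule as a sensitivity analysis.

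The cost is a second mapping rule for one time point, a few more patients counted as non-responders for a missing Day 43 film, and slightly smaller LCF/LPF denominators. The resulting ACPR proportion is conservative, so it should be read beside the Kaplan-Meier estimate. No data collection changes.

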5.2 Non-study drug antimalarials

Table 5-8 Table of non-study drug antimalarials with respective ATC codes

Non-study drug antimalarials	ATC code	ATC name
Aminoquinolines	P01BA01	Chloroquine
	P01BA02	Hydroxychloroquine
	P01BA03	Primaquine
	P01BA06	Amodiaquine
Biguanides	P01BB01	Proguanil
	P01BB02	Cycloguanil embonate
	P01BB51	Proguanil, combinations
Methanolquinoline	P01BC01	Quinine
	P01BC02	Mefloquine
Diaminopyridimidines	P01BD01	Pyrimethamine
	P01BD51	Pyrimethamine, combinations
Artemisinin and derivatives, plain	P01BE01	Artemisinin
	P01BE02	Artemether
	P01BE03	Artesunate
	P01BE04	Artemotil
	P01BE05	Artemimol
Artemisinin and derivatives, combinations	P01BF02	Artesunate and mefloquine
	P01BF03	Artesunate and amodiaquine
	P01BF04	Artesunate, sulphamethopyrazine and pyrimethamine
	P01BF05	Artemimol and piperazine
	P01BF06	Artesunate and pyronaridine
	Other Antimalarials	P01BX01
P01BX02		Arterolane and Piperazine
Coartem*	P01BF01	Artemether and lumefantrine

*in case used by patients receiving KAF156/Lum-SDF

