2.2 Analysis sets

Randomized set

All patients who are enrolled in the PK run-in cohort or randomized in Parts A and B. Unless otherwise specified, misrandomized patients will be excluded from the randomized set. For the PK run-in part, this set includes all patients with informed consent and treated with study medication.

Misrandomized patients, if identified from IRT, include patients who are screen-failures, but have been randomized by the investigator before eligibility was finally assessed or mistakenly, and have not been treated. If patients were re-screened and successfully randomized, they will be included in the randomized set according to the treatment assigned in the last randomization.

Note: There is no randomization in the PK run-in cohort. For this cohort, the more appropriate terminology is “Enrolled set”. However, ‘Randomized set’ is used for simplicity.

Full analysis set (FAS)

FAS will be comprised of all patients from Randomized set who take at least one dose of study treatment during the treatment period and whose baseline *P. Falciparum* asexual parasitemia count is greater than 0. Following the intent-to-treat principle, patients will be analyzed according to the treatment group assigned to at randomization.

Safety set (SAF)

Safety set includes all patients who take at least one dose of study drug during the treatment period. Patients will be analyzed according to treatment received. In particular, patient will be

analyzed in the same treatment group as randomized if s/he receives at least one dose of the study medication of that group.

Per-protocol set (PPS)

Per-protocol set will be comprised of patients in FAS who

- did not have any important protocol deviations
- took at least 80% of randomized study medication(s). If a patient vomited the original dose but did not vomit the replacement dose, the patient is considered as taking the dose of study medication. Since a partial compliance, such as 83%, etc., can be calculated based on the actual dosage taken (see Section 2.4.1), this allows patients assigned to KAF156 and LUM-SDF arms to take partial dosages which slightly deviates from the protocol.
- did not take non-study drug antimalarial medications prior to Day 29 unless experiencing any treatment failure (ETF, LCF, LPF) (e.g new infections between Day 8 and Day 29), and

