2.7.2.2 Treatment failure related parameters

For the following parameters, 95% confidence intervals will be provided for each treatment group using the Pearson-Clopper method:

- proportion of patients with parasitemia at 12, 24, and 48 hours after treatment
- proportion of patients with early treatment failure (ETF)
- proportion of patients with late clinical failure (LCF)
- proportion of patients with late parasitological failure (LPF)

The above parameters will be determined using the uncorrected asexual parasite counts.

In addition, patients whose outcome status cannot be determined due to incomplete/missing data will be excluded from analysis. Especially, the denominator is the number of patients who experience treatment failure or have malaria blood film result at Day 43 for LCF and LPF.

In planned analysis of PCR uncorrected ACPR at Day 29, administration of non-study antimalarial drugs without treatment failures was not considered. A sensitivity analysis will be performed to assess the impact of administration non-study antimalarial drugs on the PCR uncorrected response rate. Proportion of patients with PCR uncorrected ACPR at Day 29 with 95% CI will be re-calculated by considering the patients receiving non-study antimalarial drugs if received before Day 29 without being treatment failures as non-responder using FAS for PK Run-in, Part A and B. Patients who received concomitant prohibited non-malaria medications with potential impact on efficacy/antimalarial activity (PROH01b) before the Day 29 visit without being treatment failures will be considered as as non-responder also.

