2.7.2.3 Parasite clearance time (PCT) and fever clearance time (FCT)

Descriptive statistics (mean, standard error, median, quartiles) will be presented using the Kaplan-Meier method. Kaplan-Meier curves will be provided.

PCT will be calculated based on uncorrected asexual parasite counts. Patients without parasite clearance for whatever reason will be censored at the time of last parasite assessment. Patients who were enrolled on the basis of history of fever and did not subsequently have a fever at pre-dose will not be included in the analysis of FCT. Patients without fever clearance for whatever reason will be censored at the time of last temperature assessment. Patients who received any antimalarial medication (including rescue medication) before (parasite or fever) clearance will be censored at the first use of antimalarial medication. The difference between each test group and control will be evaluated using a log-rank test. Patients who did not experience a clearance will be censored at the time of last relevant assessment (parasite or fever). For the pooled analysis, the log-rank test will be stratified by Part.

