5.7 Rule of exclusion criteria of analysis sets

Table 5-10 Protocol deviations and non-PD criteria leading to exclusion from analysis sets

Analysis Set	PD (Description and ID) that causes Patients to be excluded	Non-PD criteria that cause Patients to be excluded
Randomized	
 Informed Consent for study participation or parental consent not obtained and patient entered trial (INCL01) 	
 Not randomized (Parts A and B) Misrandomized if identified from IRT (Parts A and B) Not treated with study medication (PK run-in part)
FAS	NA	
 Not in Randomized set; Baseline parasitemia count is 0 or missing No study drug taken
PPS	
 Parasite specie is other than Plasmodium falciparum OR mixed infection (INCL04) Baseline plasmodium falciparum parasite count <1000/uL or >=150000/uL at screening visit (INCL05) No fever within the past 24 hours at baseline (INCL07) Prohibited non-antimalarial medications that may have effect on efficacy (PROH01b) if received before the Day 29 visit without being treatment failures 	
 Not in FAS; <80% of randomized study medication taken Received non-study concomitant antimalarial drugs prior to Day 29 without experiencing treatment failure Not classified as non-responder before Day 8, no positive blood smear parasite on Day 8 onwards, and blood smear parasite result is missing at Day 29 and later (early discontinued) Not classified as non-responder before Day 8, have at least one positive blood smear parasite result between Day 8 and Day 29 which cannot be determined as recrudescence or new infection based on PCR genotyping and have parasites cleared prior to the positive blood smear parasite;

		
 Not classified as non-responder before Day 8, no positive blood smear parasite before Day 29, blood smear parasite result is missing at Day 29, and blood smear parasite result is not negative at Day 43 (intermediate missing)
SAF	NA	
 Not in Randomized set; No study drug taken
PK	Patients who received concomitant prohibited medication which found to be change in the exposure that impacts interaction in PK parameters; will be reviewed case by case for exclusion from the PK set	
 Not in SAF No evaluable pharmacokinetic parameter data Compliance is <80% of randomized study medication taken

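### SAP Table 5-8 counts artemether-lumefantrine as a non-study antimalarial only in KAF156/LUM-SDF patients, so the same outside course is handled differently in the Coartem arm

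*SAP*

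**What the plan says.** **The list.** SAP 5.2, Table 5-8, is the SAP's only list of non-study antimalarials. It includes artemether-lumefantrine (P01BF01), with a footnote limiting it: "in case used by patients receiving KAF156/Lum-SDF". No other row carries an arm restriction.

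**The rules that use the category.**
- PPS membership, SAP 2.2: the patient "did not take non-study drug antimalarial medications prior to Day 29 unless experiencing any treatment failure". Table 5-10 repeats this as an exclusion: "Received non-study concomitant antimalarial drugs prior to Day 29 without experiencing treatment failure".
- Sensitivity analysis of uncorrected ACPR at Day 29, SAP 2.7.2.2: the rate is recalculated by "considering the patients receiving non-study antimalarial drugs if received before Day 29 without being treatment failures as non-responder using FAS".
- Kaplan-Meier analyses, SAP 2.5.4.1 and 2.5.4.2: patients given non-rescue antimalarials are censored at first intake. In 2.5.4.1 the wording is narrower and refers to medication for other infections.

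**The default.** Under SAP 2.1.1.2, a patient not already a non-responder is a responder if "the patient has a malaria blood film showing absence of parasite at Day X or later if Day X is missing". Drug intake plays no part in that definition.

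**The protocol.** The PPS criterion in Protocol 9.1 excludes users of other antimalarials before Day 29, apart from rescue use, and names no arm. The Kaplan-Meier censoring in 9.4.4 and the restriction on lumefantrine-based treatment in 5.6.8.1 also make no arm exception. SAP section 4 reports no changes to the protocol's analyses.

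**The concern.** Protocol 1.2 gives Coartem two tasks: to help tell a treatment effect from a population effect when results are poor, and to give preliminary relative efficacy. Both need the same event to be handled alike in each arm. As the footnote stands, an outside course of artemether-lumefantrine changes how a test-arm patient is classified but not how a Coartem patient is.

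The Coartem arm is also inconsistent within itself. An outside course of artesunate-amodiaquine (P01BF03) triggers the rules for a Coartem patient, and an outside course of artemether-lumefantrine does not.

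Outside use is plausible. Protocol 3.4 describes Coartem as widely used, and Protocol section 4 expects about 85% of recruitment in Africa.

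**Working it through.** **1. Is there a back-stop?** Table 5-9 (prohibited medications) does not list artemether-lumefantrine. The PROH01b deviation in Table 5-10 covers non-antimalarial drugs only. Nothing else in the SAP catches an outside course in a Coartem patient.

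**2. The same patient in each arm** (no ETF, LCF or LPF; outside course before Day 29; negative film at Day 29 or later):

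| Analysis | KAF156/LUM-SDF | Coartem |
|---|---|---|
| PPS (SAP 2.2, Table 5-10) | excluded | kept, responder |
| Uncorrected ACPR Day 29 sensitivity, FAS (2.7.2.2) | non-responder | responder |
| Kaplan-Meier uncorrected ACPR (2.5.4.2), read with Table 5-8 | censored at intake | not censored |
| Kaplan-Meier PCR-corrected ACPR (2.5.4.1) | possibly censored | not censored |
| FAS supportive and secondary ACPR (2.5.4, 2.7.2.1) | intake ignored | intake ignored |
| PCT and FCT (2.7.2.3) | censored if before clearance | same |

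**3. Sample sizes.** The plan's figures reproduce: 50 × (1 − 0.16) = 42, 25 × (1 − 0.16) = 21, and 6 × 50 + 25 = 325. With 42 patients, the exact lower limit exceeds 80% from 39 responders upward, and power at a true 95% is 84.3%. The stated power of at least 80% is met.

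**4. Sensitivity analysis of uncorrected ACPR (FAS, 50 v 25).** One Coartem patient is worth 1/25 = 4.0 points if all 25 are in the FAS. Assume a true 92% in both arms (46/50 and 23/25), equal outside use, and users who would otherwise be responders. Intervals use the SAP's Wilson uncorrected method.

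| Users (test/Coartem) | As written | Difference (95% CI) | Same rule in both arms |
|---|---|---|---|
| 2 / 1 (4%) | 88% v 92% | −4.0 (−17.1 to 14.1) | 88% v 88%, 0.0 |
| 4 / 2 (8%) | 84% v 92% | −8.0 (−21.8 to 10.6) | 84% v 84%, 0.0 |
| 6 / 3 (12%) | 80% v 92% | −12.0 (−26.3 to 7.1) | 80% v 80%, 0.0 |

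**5. PPS (42 v 21).** Assume 39/42 and 20/21 before any exclusion.

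| Users (test/Coartem) | As written | Difference | Same rule in both arms | Difference | Change |
|---|---|---|---|---|---|
| 2 / 1 | 37/40 v 20/21 | −2.7 | 37/40 v 19/20 | −2.5 | 0.2 |
| 4 / 2 | 35/38 v 20/21 | −3.1 | 35/38 v 18/19 | −2.6 | 0.5 |
| 6 / 3 | 33/36 v 20/21 | −3.6 | 33/36 v 17/18 | −2.8 | 0.8 |

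For one Coartem user the control rate goes from 95.2% (20/21) to 95.0% (19/20). If every Coartem patient in the PPS responds, it does not move at all.

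**6. Kaplan-Meier.** The patient is censored, not failed, so 1/25 does not apply. As an illustration, suppose one failure occurs after the intake date. With 20 at risk the survival factor is 19/20 = 95.0%; with 19 at risk it is 18/19 = 94.7%. The effect is again tenths of a point.

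**The case against.** **The link to Table 5-8 is inferred.** The PPS, sensitivity and censoring rules do not cite the table, and their own wording is arm-neutral. The footnote was probably meant only to stop assigned Coartem being flagged. That is fair as to intent. But this is the only list of the category, and a programmer following it would exempt every artemether-lumefantrine record in the Coartem arm. The exemption is not needed for its likely purpose. Under Protocol 6.3, study doses go on the Dosage Administration Record and other drugs on the concomitant medication page.

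**The event needs several conditions.** They are an outside course despite the protocol's restriction, no treatment failure, a record of the course, and a negative film at Day 29 or later. This stands, and the frequency is unknown.

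**Stronger readings that the documents do not support:**
- *Two such patients shift every FAS comparison with Coartem by 8 points.* SAP 2.5.4 and 2.7.2.1 analyse users of non-rescue antimalarials in every arm as if they had not taken the drug. The 4 points per patient belong to the 2.7.2.2 sensitivity analysis alone. That section plans a proportion with its interval and no difference from Coartem, so the differences in step 4 are what a reader would form from the two rates.
- *Parasite and fever clearance are biased.* SAP 2.7.2.3 covers any antimalarial, rescue included: such patients "will be censored at the first use of antimalarial medication". It names no arm and applies only before clearance.
- *The primary decision is affected.* SAP 2.5.2 tests each KAF156/LUM-SDF group alone against 80%. Excluding test-arm users does matter there: 39/42 passes with a lower limit of 80.5%, while 37/40 fails at 79.6%. But that comes from the PPS rule itself, which the protocol also has, and rewording the footnote would not change it.

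**Conclusion.** The point holds within a limited scope. The footnote makes PPS membership, the uncorrected-ACPR sensitivity analysis and, on the natural reading, Kaplan-Meier censoring depend on the arm for the same event. It also departs from the protocol's PPS criterion without declaring it.

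The size is 4.0 points on the Coartem rate per affected patient in the one sensitivity analysis, and about 0.2 to 0.8 points on PPS differences for 1 to 3 Coartem users. In the sensitivity analysis the error favours Coartem; in the PPS it favours Coartem or has no effect. These figures rest on assumed counts of users, equal use in both arms, and users who would otherwise be responders.

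Only the Coartem benchmark and the exploratory comparisons are touched. The change is worth making because the sensitivity analysis exists to show the effect of non-study antimalarials, and for this drug it cannot do so in the control arm.

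**What to change.** Replace the Table 5-8 footnote with wording such as: *artemether-lumefantrine recorded as concomitant medication, and not dispensed as study drug, counts as a non-study antimalarial in all treatment groups, including Coartem.* Apply it in SAP 2.2, Table 5-10, 2.5.4.1, 2.5.4.2 and 2.7.2.2, and cite Table 5-8 in those places so that the link is explicit. Section 2.7.2.3 needs no change.

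If the arm restriction is kept, SAP section 4 should declare it as a departure from Protocol 9.1 and give the reason.

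The cost is one footnote and one programming condition, with no new data. The Coartem arm may lose one or two patients from the PPS.
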